7 STUDY INTERVENTION DISCONTINUATION AND PARTICIPANT DISCONTINUATION/WITHDRAWAL

7.1 DISCONTINUATION OF STUDY INTERVENTION

If a clinically significant finding is identified (including, but not limited to changes from baseline) after enrollment, the investigator or qualified designee will determine if any change in participant management is needed. Any new clinically relevant finding will be reported as an adverse event (AE).

AEs are evaluated according to the Division of AIDS (DAIDS) Table for Grading the Severity of Adult and Pediatric Adverse Events, version 2.1, July 2017. All adverse events will be reviewed by the Principal Investigator (PI) and the study team at team meetings. All Grade 3 events will be evaluated by the PI and the designated Medical Monitor. Grade 4 and Grade 5 events will be reported to the Sponsor and the Medical Monitor within 24 hours of notification of the event.

CD24Fc infusion will be paused for a single subject for any grade 4 event pending review by the Medical Monitor. The MM will include review of this event in a report issued to the DSMB every 12 weeks. Administration of medication will be paused for all subjects if 2 or more subjects have the same grade 4 adverse event deemed related to study drug. The MM will report these events to the DSMB and enrollment and dosing will be held for all pending review by the DSMB.

The study may be terminated after consultation with the Medical Monitor, DSMB and Sponsor, in the event that one or more of the following adverse reactions are not remediated within 2-4 hours, and in the opinion of the PI and Medical Monitor, are clinically relevant and constitute a substantial risk to the participants: cytokine release syndrome, hypotension, shortness of breath, disseminated intravascular coagulation, mental status changes.

Other criteria for study termination may include:

- the decision of the Medical Monitor or DSMB to stop further study visits
- the recommendation or decision for any reason of the PI that safety may be at risk or compromised by continuing the trial
- the decision of the Sponsor to terminate the study for any reason

The data to be collected at the time of study intervention discontinuation will include the following:

- Vital signs and physical examination
- Complete metabolic panel, complete blood count with differential, PT/INR
- Other laboratory tests that further evaluate a sign or symptom

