8.3 SAFETY AND OTHER ASSESSMENTS

Safety oversight will be conducted by collaboration between the Principal Investigator (PI), lead Study Coordinator (SC), the DSMB, and the Medical Monitor. A Medical Monitor (MM) has been appointed for

oversight of safety in this clinical study. If at any point in the trial halting rules are met, the study team (PI and SC) will arrange a (tele)conference so that the event can be reviewed and the discussion documented. At the end of each MM review meeting, the MM will be asked to provide a formal recommendation as to whether or not the protocol should be halted. A written summary of each MM review meeting will be provided to the MM and appropriate individuals. Participants on the MM teleconferences will include the MM, the PI and appropriate study team members. The MM will provide a written report to the DSMB as per Appendix A, Data Safety and Monitoring Plan (DSMP).

An independent DSMB has been established for oversight of safety in this clinical study, responsible to the NHLBI. This DSMB will be independent of regulatory agencies, IRB/EC, Oncolmmune, Inc, and investigators. See Appendix A for the Data Safety Monitoring Plan.

Subject safety will be monitored by the PI and study team. Clinical data and safety data will be monitored at least every 2 weeks (or less frequently, based on the SOA). An evaluation of safety and efficacy data will be obtained when the first 6 subjects complete 4 weeks of therapy by the appointed Medical Monitor. The Medical Monitor will not be part of the clinical staff caring for subjects during study visits, so blinding will be maintained. If concerns about the safety or efficacy arise, the Medical Monitor will refer concerns to the Sponsor and DSMB and review of adverse events will proceed per section 8 and the DSMP. Thereafter, safety and data analysis will be performed every 12 weeks through completion of the study. Additionally, the PI will be responsible for submitting the IRB Continuing Review package and will provide the necessary safety data for the FDA IND Annual Report.

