Enrollment and dosing will be paused for an individual subject who has a Grade 4 AE. After review by the Medical Monitor (MM) and reporting to the DSMB in the regularly scheduled report every 12 weeks, the MM will evaluate whether study participation for the subject should continue. During MM review, enrollment and dosing will not be paused for other study subjects.

If two subjects experience the same Grade 4 AE related to the study drug, all enrollment will be paused and all doses for enrolled subjects will be held. The MM will report to the DSMB within 24 hours and study dosing will halt until DSMB determination regarding continuation of study enrollment and dosing.

If one or more subjects experiences changes in mental status, DIC, dyspnea, cytokine release syndrome and/or hypotension related to the study drug, without remediation in 2-4 hours, the MM will report to the DSMB within 24 hours and the DSMB will review the report for possible study termination. During this review, enrollment and dosing will be halted for all subjects.

Safety and Efficacy Analyses

The primary safety endpoint will be assessed by Incidence and severity of any adverse events (AEs) during the administration of drug and 24 weeks after completion. Safety will be evaluated by assessment of clinical laboratory tests, physical examination at various time points during the study, and by the documentation for AEs. A statistical analysis plan (SAP) will be prepared and finalized prior to unblinding of subject's treatment assignment. This document will provide further details regarding the definition of analysis variables and analysis methodology to address all study objectives.

Safety and tolerability will be summarized by treatment arm, including Treatment Emergent Adverse events (TEAEs), and laboratory evaluations. No inferential analysis is planned for safety data. Adverse events will be coded using the most current version of the Medical Dictionary for Regulatory Activities

(MedDRA). TEAEs are defined as new or worsening AEs after the first dose of study medication, and will be summarized by system organ class, and preferred term. A list of subjects who have Severe Adverse Events (SAEs) and who discontinue from the study due to an adverse event will be provided.

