All statistical tests as well as the confidence intervals will be two-sided. The type I error probability for the confirmatory analysis is set to 5%. 95% confidence intervals are to be calculated, if feasible. Covariates for the primary analyses will be pre-specified. For secondary analyses these will be specified later in the SAP.

The primary efficacy and secondary analysis will be based on the mITT set. Most of primary and secondary variables such as T cell surface markers and plasma cytokine levels, and change and percent change from baseline to week 36 on markers of vascular inflammation and myocardial damages will be viewed as continuous variables and transformed as necessary. Each of efficacy variables will be analyzed using an Analysis of Covariance (ANCOVA) model with treatment as the fixed effect and other potential risk factors such as baseline value, clinical measures and demographic information as covariates. Differences between treatment groups and 95% confidence intervals will be estimated within the framework of ANCOVA. The statistical test for each of those variables will be a two-sided test at a significance level of 0.05 and no multiplicity adjustment will be done.

Timing of DSMB Meetings

Timeline	Type of Data
Prior to study dosing	Review charter, Review protocol, Select
, .	roles of DSMB members
Every Six Months	Enrollment summary, adverse events
	listings and tables for primary
	endpoints available.
Medical Monitor report	Review for determination of need for
every 12 weeks	additional DSMB review prior to next
	meeting
If two subjects have same	AE reviews, response to continue or
G4 event related to study	revert enrollment and dosing hold
drug	
If one or more subjects	Review of events with determination of
have mental status	study termination or continuance
changes, DIC, dyspnea,	
cytokine release syndrome	
or hypotension not	
remediated within 2-4	
hours and categorized as	
clinically relevant by PI and	
Medical Monitor with risk	
to participants	
Unanticipated Problem or	Review for determination of need for
non-SAE	additional DSMB review prior to next
	meeting
Upon completion or	Enrollment summary, adverse events
termination of study	listings and tables for primary
	endpoints available.

Study Termination

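### For the same unremediated acute reactions, Appendix A's halting rule and Section 7.1 (with Appendix A's DSMB table) set different trial-level triggers, and only the halting rule states a hold on dosing

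*Combined protocol and SAP*

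**What the plan says.** Four places in the combined protocol and SAP bear on this, all of them current text.

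- **Appendix A, Pausing and Halting Rules.** One subject is enough. The event must be "related to the study drug, without remediation in 2-4 hours, the MM will report to the DSMB within 24 hours". The DSMB then considers termination, and "During this review, enrollment and dosing will be halted for all subjects". The PI and Medical Monitor are not asked how important the event is.
- **Section 7.1.** The reactions and the time limit are the same, but the events must be ones that, "in the opinion of the PI and Medical Monitor, are clinically relevant and constitute a substantial risk to the participants". The consequence is discretionary: "The study may be terminated after consultation with the Medical Monitor, DSMB and Sponsor". No hold is stated. The paragraph just before it, on two or more subjects with the same drug-related Grade 4 event, does state one: "enrollment and dosing will be held for all pending review by the DSMB".
- **Appendix A, Timing of DSMB Meetings.** The row for these reactions covers events not "remediated within 2-4" hours and adds the PI and Medical Monitor's classification as clinically relevant and risky to participants. The DSMB is to decide between termination and continuation. The row mentions no hold, although the Grade 4 row does.
- **Section 8.3.** This is a general procedure for any halting rule that has been met. The study team calls a conference, and at the end of the Medical Monitor's review meeting "the MM will be asked to provide a formal recommendation as to whether or not the protocol should be halted".

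Section 8.4.9 contains only a pointer to Appendix A.

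**The concern.** Apart from open-ended decisions by the PI, Medical Monitor, DSMB or sponsor, this is the only trial-wide rule that a reaction in one participant can set off. Section 2.3.1 reports no infusion reactions so far, but it names hypotension, breathing difficulty and mental status change among the forms one could take. The rule would have to be applied within hours, by staff with no time to debate which section controls.

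Two things are at stake. One is whether other participants go on being infused while an event is under review. The other is whether a given event reaches the DSMB as a trigger at all. The inconsistency cuts both ways: one text may let dosing continue where the other stops it, and one may halt the trial for an event that the other would not escalate.

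**Working it through.** No formula applies and the plan gives no figure to reproduce. The check sets the texts side by side and runs test events through them.

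| | Appendix A, halting rule | Section 7.1 | Appendix A, DSMB table | Section 8.3 |
|---|---|---|---|---|
| Drug-relatedness required | Yes | Not explicit (speaks of adverse reactions) | No | No trigger given |
| PI and Medical Monitor judgement required | No | Yes: clinically relevant and substantial risk | Yes: clinically relevant, with risk | No trigger given |
| Trial-level hold during review | Yes | None stated | None stated | Recommendation at end of review meeting; silent on whether a hold is already in force |
| Time to report to DSMB | 24 hours | None stated (DSMB consulted before termination) | None stated | As per Appendix A |

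Three test events follow, none of them Grade 4 and all unresolved at 4 hours.

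1. **Drug-related hypotension that the PI and Medical Monitor do not judge a clinically relevant, substantial risk.** The halting rule is met, the DSMB is told within 24 hours and the trial is halted during its review. Section 7.1 is not triggered. Nor is the table, unless its unqualified mention of risk is read as a lower bar than the substantial risk in 7.1.
2. **Mental status change judged unrelated to the drug but clinically relevant and a substantial risk.** The halting rule is not met. The table row is met, and so is 7.1 unless its term adverse reactions is taken to imply relatedness. Neither states a hold.
3. **A drug-related event that is also judged a substantial risk.** All three triggers are met. The halting rule holds everyone during review, while 7.1 and the table state no hold. Section 8.3 has the Medical Monitor recommend on halting after a meeting.

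Event 1 splits the triggers. Event 3 shows that even when the triggers agree, only one text states a hold.

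The silence in 7.1 and the table carries some weight because both mention a hold for the two-subject Grade 4 rule. A reader could take its absence for these reactions as deliberate.

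The cross-reference in 8.4.9 does not settle the trigger. It leads to Appendix A, where the halting rule and the DSMB table stand together and differ.

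All three trigger statements share a further ambiguity. The limit is a range, so an event that resolves at 3 hours is unremediated at 2 hours and remediated at 4.

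**The case against.** The best defence is that Appendix A governs. Section 8.4.9 points there, and the halting rule is the only text that writes a trial-wide hold for these reactions. Section 7.1 deals with a different decision, termination, and the DSMB table lists what the board reviews rather than what happens to dosing. No text says that dosing continues. On this view the halting rule fills a gap and contradicts nothing. That largely stands for the hold: 7.1 and the table are silent, not contrary. It does not stand for the trigger, because the two conditions sit in the same appendix and select different events.

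Several stronger readings are tempting, and the documents do not support them.

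- A reader might infer four conflicting triggers. There are two: 7.1 and the table essentially agree, and 8.3 states none.
- A reader might infer from 8.3 that the halt is not automatic. That section presupposes that a halting rule has been met, and its recommendation can follow a hold already in force. It simply does not say which is meant.
- A reader might infer that an event could stop no infusion at all. Under Section 6.1.2 a severe infusion reaction stops that infusion, and under 7.1 and Appendix A any Grade 4 event pauses that subject. What can be missing is a trial-level hold.
- A reader might infer that the 24-hour report is contradicted. No text gives another time for this event. The report is in doubt only if staff apply the narrower trigger.
- A reader might picture sites following different rules. Section 8.1 places all study visits at one unit, so the risk lies in how one team reads the text.
- A reader might want a count of infusions given during an unhalted review. The documents give no length for such a review, so any count would rest on an invented duration.

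**Conclusion.** The concern holds in a limited form. For the five listed reactions not remediated within 2-4 hours, the plan has two different trial-level triggers: drug-relatedness in Appendix A's halting rule, and a PI and Medical Monitor judgement of clinical relevance and risk in Section 7.1 and the DSMB table. Only the halting rule states a hold on enrollment and dosing. Section 8.3 leaves open whether a hold is in force before the Medical Monitor makes a recommendation.

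The size is categorical. One drug-related event that the PI and Medical Monitor do not judge a substantial risk halts the trial under one text and triggers no trial-level action under the other. This assumes that the event is below Grade 4, that it is unresolved on any reading of the time limit, and that the table's mention of risk is read like the substantial risk in 7.1. It does not depend on sample size, accrual or event rates. Because the rule concerns acute participant safety, it needs correcting even though the gap is one of wording. Nothing here implies that either version is the right one.

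**What to change.** Reconcile Section 7.1, Section 8.3, the halting rule in Appendix A and the DSMB meeting table into one rule. Hold it in Appendix A and only cross-reference it from 7.1 and 8.3. The rule should state once:

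- whether the trigger is relatedness to study drug, the PI and Medical Monitor judgement, or both;
- whether enrollment and dosing are held for all subjects during review, and from what moment;
- how the Medical Monitor's recommendation in 8.3 relates to that hold;
- the time for reporting to the DSMB;
- how the 2-4 hour limit is to be read, so that an event resolving inside the range is classified one way only.

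The DSMB table row should then repeat the same trigger. The choice of version belongs to the sponsor, Medical Monitor and DSMB. The cost is a wording amendment to 7.1, 8.3 and Appendix A, with no added procedures, participants or analyses.
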